Appendix 4: Description of the iRECIST Process for Assessment of Disease Progression

Assessment at Screening and Prior to RECIST 1.1 Progression

Until radiographic progression based on RECIST 1.1, there is no distinct iRECIST assessment.

Assessment and Decision at RECIST 1.1 Progression

In participants who show evidence of radiological PD by RECIST 1.1 the Investigator will decide whether to continue a participant on study treatment until repeat imaging is obtained (using iRECIST for participant management (see Table 5 and Figures 1 and 3). This decision by the Investigator should be based on the participant's overall clinical condition.

Clinical stability is defined as the following:

- Absence of symptoms and signs indicating clinically significant progression of disease
- No decline in ECOG performance status
- No requirements for intensified management, including increased analgesia, radiation, or other palliative care

Any participant deemed clinically unstable should be discontinued from study treatment at site-assessed first radiologic evidence of PD and is not required to have repeat tumor imaging for confirmation of PD by iRECIST.

If the Investigator decides to continue treatment, the participant may continue to receive study treatment and the tumor assessment should be repeated 4 to 8 weeks later to confirm PD by iRECIST, per Investigator assessment. I

Tumor flare may manifest as any factor causing radiographic progression per RECIST 1.1, including:

- Increase in the sum of diameters of target lesion(s) identified at baseline to $\geq 20\%$ and ≥ 5 mm from nadir
 - Please note: the iRECIST publication uses the terminology “sum of measurements”, but “sum of diameters” will be used in this protocol, consistent with the original RECIST 1.1 terminology.
- Unequivocal progression of non-target lesion(s) identified at baseline
- Development of new lesion(s)

iRECIST defines new response categories, including iUPD (unconfirmed progressive disease) and iCPD (confirmed progressive disease). For purposes of iRECIST assessment, the first visit showing progression according to RECIST 1.1 will be assigned a visit (overall) response of iUPD, regardless of which factors caused the progression.

At this visit, target and non-target lesions identified at baseline by RECIST 1.1 will be assessed as usual.

New lesions will be classified as measurable or non-measurable, using the same size thresholds and rules as for baseline lesion assessment in RECIST 1.1. From measurable new lesions, up to 5 lesions total (up to 2 per organ), may be selected as New Lesions – Target. The sum of diameters of these lesions will be calculated and kept distinct from the sum of diameters for target lesions at baseline. All other new lesions will be followed qualitatively as New Lesions – Non-target.

Assessment at the Confirmatory Imaging

On the confirmatory imaging, the participant will be classified as progression confirmed (with an overall response of iCPD), or as showing persistent unconfirmed progression (with an overall response of iUPD), or as showing disease stability or response (iSD/iPR/iCR).

Confirmation of Progression

Progression is considered confirmed, and the overall response will be iCPD, if ANY of the following occurs:

- Any of the factors that were the basis for the initial iUPD show worsening
 - For target lesions, worsening is a further increase in the sum of diameters of ≥ 5 mm, compared to any prior iUPD time point
 - For non-target lesions, worsening is any significant growth in lesions overall, compared to a prior iUPD time point; this does not have to meet the “unequivocal” standard of RECIST 1.1
 - For new lesions, worsening is any of these:
 - An increase in the new lesion sum of diameters by ≥ 5 mm from a prior iUPD time point
 - Visible growth of new non-target lesions
 - The appearance of additional new lesions
- Any new factor appears that would have triggered PD by RECIST 1.1

Persistent iUPD

Progression is considered not confirmed, and the overall response remains iUPD, if:

- None of the progression-confirming factors identified above occurs AND
- The target lesion sum of diameters (initial target lesions) remains above the initial PD threshold (by RECIST 1.1)

Additional imaging for confirmation should be scheduled 4 to 8 weeks from the scan on which iUPD is seen. This may correspond to the next visit in the original visit schedule. The assessment of the subsequent confirmation scan proceeds in an identical manner, with possible outcomes of iCPD, iUPD, and iSD/iPR/iCR.

Resolution of iUPD

Progression is considered not confirmed, and the overall response becomes iSD/iPR/iCR, if:

- None of the progression-confirming factors identified above occurs, AND
- The target lesion sum of diameters (initial target lesions) is not above the initial PD threshold.

The response is classified as iSD or iPR (depending on the sum of diameters of the target lesions), or iCR if all lesions resolve.

In this case, the initial iUPD is considered to be pseudo-progression, and the level of suspicion for progression is “reset”. This means that the next visit that shows radiographic progression, whenever it occurs, is again classified as iUPD by iRECIST, and the confirmation process is repeated before a response of iCPD can be assigned.

Management Following the Confirmatory Imaging

If repeat imaging does not confirm PD per iRECIST, as assessed by the Investigator, and the participant continues to be clinically stable, study treatment may continue and follow the regular imaging schedule. If PD is confirmed, participants will be discontinued from study treatment.

NOTE: If a participant has confirmed radiographic progression (iCPD) as defined above, but the participant is achieving a clinically meaningful benefit, an exception to continue study treatment may be considered. In this case, if study treatment is continued, tumor imaging should continue to be performed following the intervals as outlined in Section 6.

Detection of Progression at Visits After Pseudo-progression Resolves

After resolution of pseudo-progression (ie, achievement of iSD/iPR/iCR), iUPD is indicated by any of the following events:

- Target lesions
 - Sum of diameters reaches the PD threshold ($\geq 20\%$ and ≥ 5 mm increase from nadir) either for the first time, or after resolution of previous pseudo-progression. The nadir is always the smallest sum of diameters seen during the entire trial, either before or after an instance of pseudo-progression.
- Non-target lesions
 - If non-target lesions have never shown unequivocal progression, their doing so for the first time results in iUPD.
 - If non-target lesions had shown previous unequivocal progression, and this progression has not resolved, iUPD results from any significant further growth of non-target lesions, taken as a whole.
- New lesions
 - New lesions appear for the first time
 - Additional new lesions appear
 - Previously identified new target lesions show an increase of ≥ 5 mm in the new lesion sum of diameters, from the nadir value of that sum

- Previously identified non-target lesions show any significant growth

If any of the events above occur, the overall response for that visit is iUPD, and the iUPD evaluation process (see Assessment at the Confirmatory Imaging above) is repeated. Progression must be confirmed before iCPD can occur.

The decision process is identical to the iUPD confirmation process for the initial PD, except in one respect. If new lesions occurred at a prior instance of iUPD, and at the confirmatory scan the burden of new lesions has increased from its smallest value (for new target lesions, their sum of diameters is ≥ 5 mm increased from its nadir), then iUPD cannot resolve to iSD or iPR. It will remain iUPD until either a decrease in the new lesion burden allows resolution to iSD or iPR, or until a confirmatory factor causes iCPD.

Additional details about iRECIST are provided in the iRECIST publication [Seymour et al., 2017].

Appendix 5: Adverse Events: Definitions and Procedures for Recording, Evaluating, Follow-up, and Reporting**14.1.1 Definition of AE****AE definition**

- An AE is any untoward medical occurrence in a clinical study participant, temporally associated with the use of study intervention, whether or not considered related to the study intervention.
- NOTE: An AE can therefore be any unfavorable and unintended sign (including an abnormal laboratory finding), symptom, or disease (new or exacerbated) temporally associated with the use of a study intervention.
- NOTE: For purposes of AE definition, study intervention (also referred to as Merck product) includes any pharmaceutical product, biological product, vaccine, diagnostic agent, or protocol specified procedure whether investigational or marketed (including placebo, active comparator product, or run-in intervention), manufactured by, licensed by, provided by, or distributed by Merck for human use in this study.

Events meeting the AE definition

- Any abnormal laboratory test results (hematology, clinical chemistry, or urinalysis) or other safety assessments (e.g., ECG, radiological scans, vital signs measurements), including those that worsen from baseline, considered clinically significant in the medical and scientific judgment of the investigator.
- Exacerbation of a chronic or intermittent pre-existing condition including either an increase in frequency and/or intensity of the condition.
- New conditions detected or diagnosed after study intervention administration even though it may have been present before the start of the study.
- Signs, symptoms, or the clinical sequelae of a suspected drug-drug interaction.
- Signs, symptoms, or the clinical sequelae of a suspected overdose of either study intervention or a concomitant medication.
- For all reports of overdose (whether accidental or intentional) with an associated AE, the AE term should reflect the clinical symptoms or abnormal test result. An overdose without any associated clinical symptoms or abnormal laboratory results is reported using the terminology “accidental or intentional overdose without adverse effect.”

Events NOT meeting the AE definition

- Medical or surgical procedure (eg, endoscopy, appendectomy): the condition that leads to the procedure is the AE.
- Situations in which an untoward medical occurrence did not occur (social and/or convenience admission to a hospital).
- Anticipated day-to-day fluctuations of pre-existing disease(s) or condition(s) present or detected at the start of the study that do not worsen.
- Surgery planned prior to informed consent to treat a pre-existing condition that has not worsened.

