6.1.2.6.5 RECIST 1.1 Assessment of Disease

RECIST 1.1 will be used as the primary measure for assessment of tumor response, date of disease progression, and as a basis for all protocol guidelines related to disease status (eg, discontinuation of study treatment). Although RECIST 1.1 references a maximum of 5 target lesions in total and 2 per organ, the Sponsor allows a maximum of 10 target lesions in total and 5 per organ, if clinically relevant to enable a broader sampling of tumor burden.

6.1.2.6.6 iRECIST Assessment of Disease

iRECIST is based on RECIST 1.1 but adapted to account for the unique tumor response seen with immunotherapeutic drugs. When clinically stable, participants should not be discontinued until progression is confirmed by the Investigator, working with local radiology, according to the rules below. This allowance to continue treatment despite initial radiologic PD takes into account the observation that some participants can have a transient tumor flare in the first few months after the start of immunotherapy, and then experience subsequent disease response.

[figure not shown]
A description of the adaptations and iRECIST process is provided in Appendix 4, with additional detail in the iRECIST publication [Seymour et al., 2017]. iRECIST will be used by the Investigator to assess tumor response and progression, and make treatment decisions.

Table 8 Imaging and Treatment after First Radiologic Evidence of Progressive Disease

	Clinically Stable		Clinically Unstable	
	Imaging	Treatment	Imaging	Treatment
First radiologic evidence of PD by RECIST 1.1	Repeat imaging at 4 to 8 weeks to confirm PD	May continue study treatment at the Investigator's discretion while awaiting confirmatory tumor imaging by site by iRECIST	Repeat imaging at 4 to 8 weeks to confirm PD per Investigator's discretion only	Discontinue treatment
Repeat tumor imaging confirms PD (iCPD) by iRECIST per Investigator assessment	No additional imaging required	Discontinue treatment (exception is possible upon consultation with Sponsor)	No additional imaging required.	Not applicable
Repeat tumor imaging shows iUPD by iRECIST per Investigator assessment	Repeat imaging at 4 to 8 weeks to confirm PD. May occur at next regularly scheduled imaging visit	Continue study treatment at the Investigator's discretion	Repeat imaging at 4 to 8 weeks to confirm PD per Investigator's discretion only	Discontinue treatment

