7.0 STATISTICAL ANALYSIS PLAN

7.1 Statistical Analysis Plan Summary

7.2 Statistical Analysis Plan

Sample size calculation: Single-Stage design will be used for this study [A'Hern, 2001; Fleming, 1982]. The study will require 48 subjects to decide whether the proportion responding (P), is less than or equal to 0.130 or greater than or equal to 0.280. If the number of responses is 10 or more, the hypothesis that $P \leq 0.130$ is rejected with a target error rate of 0.100 and an actual error rate of 0.087. If the number of responses is nine or less, the hypothesis that $P \geq 0.280$ is rejected with a target error rate of 0.100 and an actual error rate of 0.099.

Efficacy analyses: The iORR will be defined as the proportion of patients with an “immune” complete response (iCR) or “immune” partial response (iPR). For the primary iORR analysis in all the treated population, patients with an iCR or iPR will be counted as successes and all other patients (including those with missing response information) will be counted as failures. The percentage of iORR with its 95% confidence interval (CI) will be presented.

Progression free survival (PFS) will be defined among all treated patients as the time from first dose of study drug until the first date of either disease progression or death due to any cause. The date of disease progression will be defined as the earliest date of disease progression based on central review. For patients whose disease has not progressed at the time of the analysis, censoring will be performed using the date of the last valid disease assessment. The data will be analyzed by the Kaplan-Meier method. The median PFS time and 95% CI will be recorded.

Overall survival (OS): Median OS will be defined as the time from the beginning of study drug treatment until death due to any cause. For patients who have not died at the time of the analysis, censoring will be performed using the date the patient was last known to be alive. The data will be analyzed by the Kaplan-Meier method. The median OS and 95% CI will be recorded.

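### Under Appendix 4, unconfirmed progression caused only by new or non-target lesions that then stay unchanged must become iSD or iPR, and Section 7.2 counts that iPR as a success

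*Combined protocol and SAP*

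**What the plan says.** Appendix 4 assigns iUPD at the first visit with RECIST 1.1 progression, "regardless of which factors caused the progression". The causes it lists are growth of the baseline target lesions, unequivocal non-target progression and new lesions. Diameters of new lesions are summed separately from those of the baseline target lesions.

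At the confirmatory scan, further worsening of a triggering factor, or any new factor that would itself be RECIST 1.1 progression, gives iCPD. If neither occurs, iUPD persists when "The target lesion sum of diameters (initial target lesions) remains above the initial PD threshold (by RECIST 1.1"). It resolves when that same sum is not above the threshold. After resolution, "The response is classified as iSD or iPR (depending on the sum of diameters of the target lesions), or iCR if all lesions resolve". The episode is then treated as pseudo-progression, and the next progression starts a new iUPD.

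Section 7.2 defines the primary iORR analysis: "patients with an iCR or iPR will be counted as successes". It makes no exception for an iPR reached after iUPD. The design tests whether the response proportion is "less than or equal to 0.130 or greater than or equal to 0.280", with 48 patients and success declared at 10 or more responses.

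**The concern.** iUPD can have three kinds of cause, but the test that separates persistence from resolution looks at only one of them. Suppose the target lesions have shrunk enough for a partial response while a new metastasis appears. The scan is iUPD. If both findings are unchanged at the repeat scan, the patient becomes iPR and is a success, although nothing about the new lesion has improved.

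The pembrolizumab benchmark in Section 4.1.1, 12.2% in 98 patients, came from RECIST 1.1 with blinded independent central review. Appendix 4 itself lists new lesions as a cause of RECIST 1.1 progression. Comparing an iORR built on the more permissive rule with that rate favours the combination. The decision margin is one patient: 9 responses reject the 28% hypothesis and 10 reject the 13% hypothesis.

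**Working it through.** **The rule.** All combinations at the confirmatory scan, from Appendix 4:

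| Confirming factor present | Initial target sum above PD threshold | Category |
|---|---|---|
| No | No | iSD or iPR (iCR only if all lesions resolve) |
| No | Yes | iUPD persists |
| Yes | No | iCPD |
| Yes | Yes | iCPD |

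When a new or non-target lesion alone caused the iUPD, the target sum was not above the threshold to begin with. If nothing changes, the patient is in the first row. Persistent iUPD cannot be reached.

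**The plan's own figures.** The inputs from Section 7.2 are n = 48, a cut-off of 10, a null rate of 0.13 and an alternative of 0.28. With X binomial(48, p):

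- P(X ≥ 10 | p = 0.13) = 0.0865, stated as 0.087.
- P(X ≤ 9 | p = 0.28) = 0.0995 (0.09946 before rounding), stated as 0.099.

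Both agree.

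**Sensitivity to the rule.** Let d be the proportion of all patients who become responders only through this route. The documents do not give d, so the values below are assumptions. The error is P(X ≥ 10 | p = 0.13 + d).

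| d (percentage points) | Expected patients, 48 × d | P(X ≥ 10) |
|---|---|---|
| 0 | 0 | 0.087 |
| 0.5 | 0.24 | 0.105 |
| 1 | 0.48 | 0.126 |
| 2 | 0.96 | 0.174 |

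The 0.100 target is passed between d = 0.35 (0.0993) and d = 0.40 (0.1012).

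**Who is affected.** The patient must be re-imaged after the iUPD, must have a target sum that meets the partial-response criterion, must show no further new or non-target growth, and must not already have had a qualifying iPR before the iUPD. A patient with an earlier qualifying iPR is a success in any case.

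**The case against.** The strongest reply is that this is a design choice. Section 2.0 says new lesions alone are not progression. Appendix 4 openly provides for non-target progression that is still unresolved after pseudo-progression has been declared resolved. It also defers further detail to the iRECIST publication, which is not part of the documents. That is a fair reason not to call the rule a mistake. It does not settle whether such a patient should count towards a primary endpoint read against a RECIST 1.1 rate.

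Several stronger readings are tempting, and the documents do not support them.

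- A reader might infer that resolution ignores everything except target lesions. It does not. It also requires no worsening of new or non-target disease; what it lacks is any requirement that they improve.
- A reader might see a contradiction with Section 6.1.2.6.6, which notes that "some participants can have a transient tumor flare in the first few months after the start of immunotherapy, and then experience subsequent disease response". That sentence is a rationale and sets no criterion.
- A reader might see an asymmetry with the provision for later episodes, where iUPD holds "until either a decrease in the new lesion burden allows resolution to iSD or iPR". That provision applies when the new-lesion burden has increased. Unchanged lesions are not covered in any episode.
- A reader might conclude that the reset carries patients past the 20-week iPFS landmark. Take a new lesion at week 9, unchanged at weeks 13 to 17 and growing at week 18. With the reset, iUPD falls at week 18 and iCPD at weeks 22 to 26. Without it, the week-18 growth confirms the week-9 iUPD. The landmark is crossed only if iPFS is dated at iCPD. Dated at iUPD, the event is week 18 or week 9, both before week 20. Section 7.2 does not say which date applies.
- A reader might treat one extra responder as lowering the cut-off to 9, with error 0.164. That assumes one such conversion in every trial.

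Section 6.1.2.6.2 also asks for a scan at least four weeks later to confirm a response. This narrows the group but does not close the gap, because it says nothing about persisting new or non-target lesions.

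**Conclusion.** The point stands as a gap in the definition of a primary-endpoint success. By the text of Appendix 4, iUPD driven solely by new or non-target lesions that stay unchanged becomes iSD or iPR, and Section 7.2 counts the iPR. The possible bias in iORR is upward.

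Its size cannot be established from the documents. Under the assumed range of 0.5 to 2 points on a true 13% rate, the error rises from 0.087 to between 0.105 and 0.174, so a small frequency is enough to exceed the 0.100 target. This rests on iRECIST governing the primary endpoint, as Sections 3.1 and 7.2 state. Section 6.1.2.6.5 instead names RECIST 1.1 as the primary measure of response, and that also needs reconciling.

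**What to change.** Confine the change to the analysis, in Section 7.2. State that an iPR first reached after an iUPD driven by new or non-target lesions counts as a success only if those lesions have regressed or resolved on scans already taken. At minimum, pre-specify a sensitivity iORR that counts such patients as failures, and report whether the 10-of-48 decision changes. State also whether iPFS is dated at first iUPD or at iCPD, and whether an iUPD that was later reset counts as an event.

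The cost is a few sentences and no new imaging. The response count can only fall, and the rule is stricter than Appendix 4 as written. If the 28% alternative was meant to include such cases, excluding 1 or 2 points lowers power from 0.901 to P(X ≥ 10 | p = 0.27) = 0.872 or P(X ≥ 10 | p = 0.26) = 0.837.

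No rewrite of the Appendix 4 rule for patient management is proposed here. A reader might think it could be changed without touching treatment, but Table 8 links iUPD, iCPD and iSD/iPR/iCR to different treatment actions, and for clinically unstable patients it separates repeat iUPD from iSD/iPR/iCR. The sponsor should reconcile the resolution rule with Section 2.0 (new lesions added to total burden), Table 8 and Appendix 4's own provision for later iUPD episodes.

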14.1.2 Definition of SAE

If an event is not an AE per definition above, then it cannot be an SAE even if serious conditions are met.

An SAE is defined as any untoward medical occurrence that, at any dose:

a. Results in death**b. Is life-threatening**

- The term “life-threatening” in the definition of “serious” refers to an event in which the participant was at risk of death at the time of the event. It does not refer to an event, which hypothetically might have caused death, if it were more severe.

c. Requires inpatient hospitalization or prolongation of existing hospitalization

- Hospitalization is defined as an inpatient admission, regardless of length of stay, even if the hospitalization is a precautionary measure for continued observation. (Note: Hospitalization for an elective procedure to treat a pre-existing condition that has not worsened is not an SAE. A pre-existing condition is a clinical condition that is diagnosed prior to the use of a Merck product and is documented in the participant’s medical history.)

d. Results in persistent or significant disability/incapacity

- The term disability means a substantial disruption of a person’s ability to conduct normal life functions.
- This definition is not intended to include experiences of relatively minor medical significance such as uncomplicated headache, nausea, vomiting, diarrhea, influenza, and accidental trauma (eg, sprained ankle) that may interfere with or prevent everyday life functions but do not constitute a substantial disruption.

e. Is a congenital anomaly/birth defect

- In offspring of participant taking the product regardless of time to diagnosis.

f. Other important medical events

- Medical or scientific judgment should be exercised in deciding whether SAE reporting is appropriate in other situations such as important medical events that may not be immediately life-threatening or result in death or hospitalization but may jeopardize the participant or may require medical or surgical intervention to prevent 1 of the other outcomes listed in the above definition. These events should usually be considered serious.
- Examples of such events include invasive or malignant cancers, intensive treatment in an emergency room or at home for allergic bronchospasm, blood dyscrasias or convulsions that do not result in hospitalization, or development of drug dependency or drug abuse.

